### **5.5.3 Patient Disposition**

Data tabulations will summarize the following patient numbers:

- Enrolled
- HBI-8000 treatment dose received
- Evaluable for safety and efficacy
- Protocol violations
- Protocol completions
- Withdraw from study due to:
  - AE
  - Physician's recommendation
  - Withdrew consent
  - Lost to follow-up
  - Other reasons as collected on the eCRF

## **5.6 Patient Characteristics**

Demographic and baseline characteristics of patients will be summarized using descriptive statistics:

- Age
- Gender
- Race
- Ethnicity
- ECOG Performance Status
- Prior therapies
- Other baseline characteristics as collected on the eCRF.

## **5.7 Concomitant Medications**

The number and proportion of patients using different concomitant medications will be tabulated and summarized by WHO Drug anatomical therapeutic chemical classification system and preferred term.

## **5.8 Treatment Administration**

Study drug administration will be described in terms of the total number of cycles administered, the median (range) of cycles administered, dose intensity, and reasons for the deviations from planned therapy.

## **5.9 Efficacy Analysis**

The efficacy endpoints are the following:

Primary Endpoint:

- ORR; CR + CRu + PR

Secondary Endpoints:

- ORR by disease subtype (acute, lymphoma, and unfavorable chronic type)
- Median duration of PFS
- Median DOR

Exploratory Endpoint

- Median duration of OS

Response rate endpoints (ORR and ORR by disease subtype) will be summarized by number and percentage of patients meeting the definition of ORR along with the corresponding exact

95% CI. Tumor response as assessed by imaging studies will be adjudicated by independent radiology reviewers. Tumor lesions, such as skin lesion, that cannot be monitored by imaging studies will be determined by independent oncology reviewers and contributed to overall disease response assessment. Both investigators reported and independently adjudicated outcomes will be reported.

Primary analysis will be based on results from imaging studies and clinical data confirmed by Independent Central Review. Results from investigator assessment will also be reported.

Time-to event endpoints (PFS, DOR, and OS) will be summarized by Kaplan-Meier methods (median, 95% CI, number of events, number censored and Kaplan-Meier figures).

## **5.10 Safety Analysis**

All patients who receive 1 dose (any amount) of HBI-8000 will be included in the summaries and listings of safety data. Overall safety profile and tolerability will be characterized by type, frequency, severity, timing, duration and relationship of study therapy of AEs and laboratory abnormalities.

### **5.10.1 Adverse Events**

AEs will be classified using the MedDRA classification system version 19.0 or higher. The severity of the toxicities will be graded according to the NCI CTCAE version 4.03.

In all summaries, emphasis will be placed on treatment-emergent adverse events (TEAEs), namely, those with initial onset or that worsen in severity after the first dose of HBI-8000. TEAEs will be summarized by the frequency of patients experiencing TEAEs corresponding to body systems and MedDRA preferred term and by worst NCI CTCAE (version 4.03) Grade. Summaries will also be provided of treatment-related TEAEs, namely, those judged by the investigator to be related or likely related to HBI-8000.

TEAEs resulting in discontinuation of HBI-8000 treatment or withdrawal from the study, Grade 3 or higher, SAEs, and deaths on-study will be tabulated.

### **5.10.2 Laboratory Tests**

Laboratory data will be summarized for the observed values at each scheduled assessment, together with the corresponding changes from baseline (the value obtained prior to dosing on Day 1 of Cycle 1) using descriptive statistics.

For those analyses with CTCAE Grades, abnormal laboratory values will be summarized by shift tables displaying numerical values and percentages classified by baseline grade (e.g., Grade prior to dosing on Day 1 of Cycle 1) and maximum grade on treatment. All laboratory data will be presented in listings.

### **5.10.3 ECGs**

Serial ECGs will be performed to evaluate the potential effects of the study drug on the heart. The ECG parameters (PR interval, QRS duration, QT, QTc and QTcF) will be summarized descriptively for each time point for both the observed values and the change from baseline

to each post-baseline time point. The number and percentage of patients with QT or QTc (QTcF) outlier values (at any post-baseline time point), as defined in ICH E14, will be summarized.

#### **5.10.4 Vital Signs and Physical Findings**

Vital signs data will be summarized by the observed values at each scheduled assessment, together with the corresponding changes from baseline using descriptive statistics.

Physical findings will be presented in data listings.

#### **5.10.5 Interim Analysis**

No interim analysis for efficacy is planned for this Phase 2b study.

## **6.0 ETHICS**

### **6.1 Institutional Review Board or Independent Ethics Committee**

The protocol, ICF and any other written information and/or materials to be provided to the patients and the amendments (as required by local regulations) should be reviewed and approved by the IRB/Independent Ethics Committee (IEC). The sponsor's authorized representative should be provided with documentation of IRB/IEC approval of the protocol and informed consent before the study may begin at the study center(s).

The only circumstance in which an amendment may be initiated prior to the sponsor and IRB/IEC approval is where the change is necessary to ensure the safety of the patients. In that case, the investigator must document the change and notify the sponsor and IRB/IEC in writing immediately after the implementation.

The investigator should submit written summaries of the study status for review by the IRB/IEC annually, or more frequently if requested by the IRB/IEC. Upon completion of the study, the investigator will provide a brief report of the outcome of the study, if required. The sponsor and/or the sponsor's authorized representative will handle the distribution of any of these documents to the national regulatory authorities.

### **6.2 Ethical Conduct of the Study**

This study will be conducted and the informed consent will be obtained according to the ethical principles stated in the Declaration of Helsinki (48th General Assembly, Somerset West, Republic of South Africa, October 2008 [or current version]), the applicable guidelines for GCP (CPMP/ICH/135/95), or the applicable drug and data protection laws and regulations of the countries where the study will be conducted.

GCP is an international ethical and scientific quality standard for designing, conducting, recording and reporting studies that involve the participation of human patients. The study will be conducted in compliance with GCP and the applicable national regulations so as to assure that the rights, safety and well-being of the participating study patients are protected consistent with the ethical principles that have their origin in the Declaration of Helsinki.

### **6.3 Patient Information and Informed Consent**

The ICF will be used to explain the risks and benefits of study participation to the patient in simple terms before the patient will be entered into the study. The ICF contains a statement that the consent is freely given, that the patient is aware of the risks and benefits of entering the study, and that the patient is free to withdraw from the study at any time. Written consent must be given by the patient and/or the legal guardian, after the receipt of detailed information on the study.

The investigator is responsible for ensuring that informed consent is obtained from each patient or the legal guardian and for obtaining the appropriate signatures and dates on the informed consent document prior to the performance of any protocol procedures and prior to

the administration of study medication. The investigator will provide each patient with a copy of the signed and dated consent form.

Whenever important new information becomes available that may be relevant to the patient's consent, the approved by the IRB/IEC, revised information will be provided to each patient in the trial for signing and dating. The investigator will explain the changes to the previous version.

#### **6.4 Patient Data Protection**

The ICF will incorporate (or, in some cases, be accompanied by a separate document incorporating) wording that complies with relevant data protection and privacy legislation. Information about study subjects will be kept confidential and managed according to the regulatory requirements.

## **7.0 STUDY ADMINISTRATION**

### **7.1 Administrative Structure**

The administrative structure and study organization is presented in protocol addendum.

### **7.2 Data Handling and Record Keeping**

It is the investigator's responsibility to maintain essential study documents (protocol and protocol amendments, completed eCRFs, signed ICFs, relevant correspondence, and all other supporting documentation). The study site should plan on retaining such documents for approximately 15 years after study completion. The study site should retain such documents until at least 2 years after the last approval of a marketing application in an ICH region and until there are no pending or contemplated marketing applications in an ICH region or at least 2 years after the formal discontinuation of clinical development of the investigational product. These documents should be retained for a longer period if required by the applicable regulatory requirements or the hospital, institution, or private practice in which the study is being conducted. Patient identification codes (patient names and corresponding study numbers) will be retained for this same period of time. These documents may be transferred to another responsible party, acceptable to sponsor, who agrees to abide by the retention policies. Written notification of transfer must be submitted to the sponsor and/or the sponsor's authorized representative. The investigator must contact the sponsor and/or the sponsor's authorized representative prior to disposing of any study records.

The U.S. FDA regulations (21 CFR §312.62[c]) and the ICH Guideline for GCP (see Section 4.9 of the guideline) require that records and documents pertaining to the conduct of this study and the distribution of study drug, including eCRFs, consent forms, laboratory test results, and medication inventory records, must be retained by the principal investigator for 15 years after the last marketing application approval in an ICH region or after at least 15 years have elapsed since formal discontinuation of clinical development of the investigational drug.

No records should be disposed of without the written approval of the sponsor and/or the sponsor's authorized representative.

For studies conducted outside the United States under a U.S. investigational new drug (IND), the principal investigator must comply with U.S. FDA IND regulations and with those of the relevant national and local health authorities.

### **7.3 Direct Access to Source Data/Documents**

The investigator will prepare and maintain adequate and accurate source documents to record all observations and other pertinent data for each patient enrolled into the study.

The investigator will allow the sponsor, the sponsor's authorized representative(s), and authorized regulatory authorities to have direct access to all documents pertaining to the study, including individual patient medical records, as appropriate.

## **7.4 Investigator Information**

### **7.4.1 Investigator Obligations**

This study will be conducted in accordance with the ICH Harmonized Tripartite Guideline for GCP (GCP, 1997; the US CFR Title 21 parts 50, 56, and 312; European Legislation; and Ministerial Ordinance on the Standards for the Implementation of Clinical Studies on Pharmaceutical Product [Japan GCP]) and the ethical principles that have their origin in the Declaration of Helsinki, and the applicable regulatory requirements of each region.

The investigator agrees to conduct the clinical study in compliance with this protocol after the approval of the protocol by the IEC/IRB in compliance with local regulatory requirements. The investigator and the sponsor will sign the protocol to confirm this agreement.

### **7.4.2 Protocol Signatures**

After reading the protocol, each investigator will sign the protocol signature page and send a copy of the signed page to the sponsor or representative ([Appendix F](#)). By signing the protocol, the investigator confirms in writing that he/she has read, understands and will strictly adhere to the study protocol and will conduct the study in accordance with ICH Tripartite Guidelines for GCP and applicable regulatory requirements. The study will not be able to start at any site where the investigator has not signed the protocol.

### **7.4.3 Publication Policy**

The data generated by this study are confidential information of the sponsor. The sponsor will make the results of the study publicly available. The publication policy with respect to the investigator and study site will be set forth in the Clinical Trial Agreement.

## **7.5 Financing and Insurance**

The sponsor has obtained liability insurance, which covers this study as required by local law and/or national regulations and/or ICH guidelines whichever is applicable. The terms of the insurance will be kept in the study files.

## 9.0 APPENDICES

### 9.1 Appendix A: HBI-8000-210 Schedule of Events

**Table 4: Schedule of Events**

	Screening	Cycle 1				Cycle 2		Cycle $\geq 3$ a	EoT b	Survival F/U c
DAY	-28 to 0	1	8 ± 2	15 ± 2	22 ± 2	1 ± 4	15 ± 4	1 ± 7		
		Pre-dose d	3.5 hrs			Pre-dose	3.5 hrs		Pre-dose	
HBI-8000 d,e		BIW f				BIW f		BIW f		
Written informed consent	X									
Medical history, diagnosis and treatment history, demographics, height	X									
Physical examination, weight	X	X		X		X		X	X	
ECOG Performance Status	X	X				X			X	X
Vital signs g	X	X		X		X		X	X	
12 Lead ECG (Safety)	X							X	X	
12 Lead ECG (QTc) h		X	X			X	X			
Hematology i	X	X		X	X	X		X	X	
Coagulation j	X	X		X		X			X	
Chemistry k	X	X		X	X	X		X	X	
Urinalysis l	X	X								X
Hepatitis B/C virus, and HTLV-I Antibody tests m	X									
Serum pregnancy test (if applicable) n	X	X							X	
Tumor assessment o	X					X		X o	X o	X o
Patient survival; new cancer therapies										X
Adverse events assessment	X	X		X	X	X		X	X	X
Concomitant medication	X	X		X	X	X		X	X	X

Abbreviations: ALT, alanine aminotransferase; aPTT, activated partial thromboplastin time; AST, aspartate aminotransferase; BIW, twice weekly; BUN, blood urea nitrogen; ECG, electrocardiogram; ECOG, Eastern Cooperative Oncology Group; EoT, end of treatment; F/U, follow-up; GGT, gamma-glutamyl transpeptidase; INR, international normalized ratio; LDH, lactate dehydrogenase; mSWAT, Modified Severity-Weighted Assessment Tool; PCR, polymerase chain reaction; PT, prothrombin time;

- a Cycle/Day designation is based on actual calendar days after the first dose. All visits and assessments may be performed  $\pm$  7 days to accommodate unforeseen delays, holidays, or vacations.
- b “End of Treatment” visit should be conducted  $30 \pm 3$  days after the last dosing of the study drug, or before the initiation of new cancer treatment, whichever is earlier.
- c Survival data will be collected every 3 months  $\pm$  2 weeks after EoT until death or the end of the study, defined as 12 months after the administration of the last dose of the entire study.
- d On the days of scheduled visits that is the same as the dosing scheduled day, patient should take study drug after receiving confirmation from investigator to continue study treatment.
- e Drug administration BIW for 4 weeks
- f Dose adjustments based on hematological and non-hematological criteria.
- g Pulse rate, diastolic and systolic blood pressure in seated position of 5 minutes. On days when ECGs are taken, vital signs to be taken shortly prior to ECG recording.
- h Pre-dose, and post-dose at  $3.5 \pm 0.5$  hours in triplicates, 5  $\pm$  2 minutes between 1st and 2nd, 2nd and 3rd ECGs, on C1D1 and C2D1
- i Hemoglobin, hematocrit, red blood cell count, white blood cell count, differential, platelet count.
- j Coagulation tests (PT, aPTT, and INR).
- k BUN, creatinine, AST, ALT, GGT, total bilirubin (including direct fraction if total bilirubin abnormal), lipase, amylase, total protein, albumin, alkaline phosphatase, sodium, potassium, calcium, magnesium and random blood glucose, LDH, CKMB
- l Urinalysis (glucose, protein, occult blood) will be performed by dipstick method, and in the event of abnormal dipstick results, additional test may be required..
- m Hepatitis B surface antigen, hepatitis B core antibody, hepatitis B surface antibody and hepatitis C virus antibody will be analyzed at screening. Hepatitis B surface antigen-positive or hepatitis C virus antibody positive patients are excluded from the study. In case hepatitis B core antibody and/or hepatitis B surface antibody is positive even if hepatitis B surface antigen negative, a hepatitis B virus DNA test (real-time PCR measurement) should be performed and if positive, the patient should be excluded from the study.
- n Only for women of childbearing potential, including those who have had a tubal ligation. Confirmatory test at the C1D1 visit should be done before dosing at the local laboratory. If Serum pregnancy test result cannot be obtained on the same day before dosing, urine pregnancy test should be conducted additionally and the result should be confirmed before dosing. Only at EoT visit, Serum and Urine are both acceptable.
- o Complete tumor assessment of all lesions by radiographic or other modality. Response and progression for ATL will be evaluated according to the International Consensus Meeting [[Tsukasaki 2009](#)]. CT or MRI of the chest, abdomen, and pelvis to evaluate disease in these locations. CT/MRI of the head at screening for patients who are suspected to have CNS metastases. Assessment of tumor response will be scheduled by end of the 4th week, the 8th week, then every 8 weeks ( $\pm$  1 week) from C3D1. However, if a patient develops clinical signs and symptoms of PD, or unacceptable toxicity occurs, tumor assessment may be performed sooner as needed. If a patient discontinues study treatment before PD is recorded, and if their last tumor assessment was  $>30$  days earlier from EoT visit, tumor assessment should be performed at EoT. In these patients, further tumor assessments are to be performed approximately every 3 months  $\pm$  2 weeks until PD or the start of new cancer therapy whichever occurs first, unless consent to study participation is withdrawn.

- p Some of the pre-dose assessments except vital signs and ECG may be performed one day before C1D1 to accommodate scheduling requirements in the hospital.

## 9.2 Appendix B: Eastern Cooperative Oncology Group (ECOG) Performance Status

**Table 5: Eastern Cooperative Oncology Group (ECOG) Performance Status**

ECOG Grade	ECOG Status
0	Fully active, able to carry on all pre-disease performance without restriction
1	Restricted in physically strenuous activity but ambulatory and able to carry out work of a light or sedentary nature, e.g., light house work, office work
2	Ambulatory and capable of all selfcare but unable to carry out any work activities. Up and about more than 50% of waking hours
3	Capable of only limited selfcare, confined to bed or chair more than 50% of waking hours
4	Completely disabled. Cannot carry on any selfcare. Totally confined to bed or chair
5	Dead

Source: Oken, M.M., Creech, R.H., Tormey, D.C., Horton, J., Davis, T.E., McFadden, E.T., Carbone, P.P.: Toxicity And Response Criteria Of The Eastern Cooperative Oncology Group. Am J Clin Oncol 5:649-655, 1982.

### 9.3 Appendix C: New York Heart Association (NYHA) Classification

Table 6: New York Heart Association (NYHA) Classification

Class	Patient Symptoms
I	No limitation of physical activity. Ordinary physical activity does not cause undue fatigue, palpitation, dyspnea (shortness of breath).
II	Slight limitation of physical activity. Comfortable at rest. Ordinary physical activity results in fatigue, palpitation, dyspnea (shortness of breath).
III	Marked limitation of physical activity. Comfortable at rest. Less than ordinary activity causes fatigue, palpitation, or dyspnea.
IV	Unable to carry on any physical activity without discomfort. Symptoms of heart failure at rest. If any physical activity is undertaken, discomfort increases.

Adapted from Farrell MH et al. JAMA. 2002; 287:890-897

- (1) Raphael C et al. Limitations of the New York Heart Association functional classification system and self-reported walking distances in chronic heart failure. Heart. 2007;93(4):476-82
- (2) MeReC Bulletin 2008; 18 (3):1-9.
- (3) National Institute for Health and Clinical Excellence (NICE) 2010. Chronic heart failure. National clinical guideline for diagnosis and management in primary and secondary care

## **9.4 Appendix D: Tumor Response Criteria**

### **9.4.1 Method of Efficacy Assessment**

Overall response will be assessed based on evaluation at screening and post-dose evaluation including complete tumor response assessments (peripheral blood, skin lesions, nodal and extranodal lesions) and on Day 1 of subsequent cycles for peripheral blood and skin lesions. Imaging studies such as CT to evaluate nodal and extranodal lesions will be performed by end of the 4th week, the eighth week, then every 8 weeks ( $\pm$  1 week) from C3D1. However, if a patient develops clinical signs and symptoms of PD, or unacceptable toxicity occurs, tumor assessment may be performed sooner as needed. If a patient discontinues study treatment before PD is recorded, and if their last tumor assessment was  $>30$  days earlier from EoT visit, tumor assessment should be performed at EoT. In these patients, further tumor assessments are to be performed approximately every 3 months  $\pm$  2 weeks until PD or the start of new cancer therapy whichever occurs first, unless consent to study participation is withdrawn.

### **9.4.2 Evaluation at Screening**

At screening, lesion will be evaluated by imaging (CT), hematology test (white blood cell [WBC] count, absolute lymphocyte count, and abnormal lymphocyte count (% and absolute count) and bone-marrow test (bone-marrow aspiration or biopsy). In case gastrointestinal lesion is suspected, endoscopy and biopsy (as needed) will be performed.

All lesions are categorized into the following:

- lesion which can be used for efficacy assessment (hereinafter, evaluable lesion)
- lesion which cannot be used for efficacy assessment (hereinafter, non-evaluable lesion)

[figure not shown]
In addition, evaluable lesions are categorized into the following:

- measurable lesion
- non-measurable lesion

Next, target lesions (up to 6 lesions) are selected from measurable lesions.

Non-measurable lesions and other measurable lesions are deemed as non-target lesions.

**Figure 3: Selection of Lesions**

#### **9.4.2.1 Evaluation of Nodal Lesion and Extranodal Lesion**

Evaluation of nodal lesion and extranodal lesion will be performed according to the Criteria for Adult T-Cell Leukemia-Lymphoma ([Tsukasaki 2009](#)).

The definition of nodal and extranodal lesion is as following:

- Nodal lesion: lymphoma that developed in lymph node and lymph tissue (amygdala, thymus, spleen, and Peyer's patch in small bowel)
- Extranodal lesion: lymphoma that developed in non-lymphoid organ or tumor mass.

##### **9.4.2.1.1 Imaging**

Before the start of study drug administration, evaluation by CT images of neck, chest, abdomen, and groin that are taken by a pitch of 1 cm or less (as for neck image, a pitch of 5 mm or less will be preferred) will be performed. As a general rule, contrast enhanced CT should be used. However, in case contrast enhanced CT cannot be performed because the subject has a history of adverse drug reaction caused by contrast agent or a current history of renal dysfunction, and in case the lesions of the subject are evaluable by non-contrast enhanced CT, plain CT is permitted.

If evaluation by other imaging is needed according to the type of lesion, additional imaging will be permitted (e.g., MRI).

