#### **9.4.2.1.4      Definition of Measurable Lesion (common with nodal and extranodal lesion)**

In evaluable lesions, measurable lesion is defined as the lesion that meets both following criteria:

- The size by Long dimension over 1.5 cm on sectional image of CT
- Definitely measurable by 2 orthogonal dimensions (long dimension and its orthogonal dimension) on sectional image of CT

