### 9.4.3 Post-dose Evaluation

#### 9.4.3.1 Evaluation of nodal and extranodal lesion

Computed tomography imaging will be performed by the same method as screening.

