##### 9.4.3.1.1 Evaluation of target lesion

Efficacy for target lesion will be assessed by calculating reduction rate (A) and growth rate (B) of the sum of 2-dimension products according to the following formula:

$$(A) = \frac{(C) \text{ at screening} - (C) \text{ at evaluation}}{(C) \text{ at screening}} \times 100$$

$$(B) = \frac{(C) \text{ at evaluation} - \text{minimum } (C)}{\text{minimum } (C)^{*1}} \times 100$$

\*1: minimum (C) value obtained during the study including the screening

(C) = sum of 2-dimension products

Criteria for assessment of anti-tumor effect on target lesion are as follows:

CR: Absence of enlarged lymph node, AND disappearance of all extranodal lesions.

CRu: Reduction rate of the sum of 2-dimension products of  $\geq 75\%$ , but presence of residual lesion

PR: Reduction rate of the sum of 2-dimension products of  $\geq 50\%$  and  $< 75\%$

SD: Effect not reached PR, but not PD

PD: Growth rate of the sum of 2-dimension products of  $\geq 50\%$

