##### 9.4.3.1.2 Evaluation of nodal non-target lesion

Criteria for assessment of tumor shrinkage effect on nodal non-target lesion are as follows:

Normal: Absence of enlarged lymph node (long dimension over 1.5 cm) in any lymph node area.

Non-growth: Presence of enlarged lymph node, but absence of enlarged lymph node which showed apparent growth\*2 in comparison with minimum value on and after screening

Growth: Presence of enlarged lymph node which showed apparent growth\*2 in comparison with minimum value on and after screening

Non-evaluable: Presence of lymph node area which cannot be evaluated

\* Apparent growth is, only as a guide, the growth of long dimension  $\geq 50\%$ , but measurement on image is not necessary.

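### With CT spacing of up to 1 cm and one 1.5 cm cut-off for both measurability and nodal CR, slice position alone can make an unchanged node of about 1.5 to 1.8 cm read as nodal CR

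*Combined protocol and SAP*

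**What the plan says.** All the relevant text is in Appendix D of the protocol.

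- **Spacing.** Section 9.4.2.1.1 covers neck, chest, abdomen and groin, with images "taken by a pitch of 1 cm or less (as for neck image, a pitch of 5 mm or less will be preferred". The finer spacing is thus a preference, and for the neck only. No slice thickness is given.
- **Later scans.** Section 9.4.3.1: "Computed tomography imaging will be performed by the same method as screening". This repeats the technique but cannot fix where a section falls on a node.
- **Entry size.** Section 9.4.2.1.4 sets the measurable limit: "The size by Long dimension over 1.5 cm on sectional image of CT", together with two clearly measurable orthogonal dimensions.
- **CR.** Section 9.4.3.1.1 for target lesions: "CR: Absence of enlarged lymph node, AND disappearance of all extranodal lesions". Section 9.4.3.1.2 gives the size that counts as enlarged: "Normal: Absence of enlarged lymph node (long dimension over 1.5 cm) in any lymph node area". No percentage reduction is attached, whereas PR needs a fall of at least 50% in the summed products.
- **PD.** Section 9.4.3.1.1: "PD: Growth rate of the sum of 2-dimension products of" 50% or more, measured against the "minimum (C) value obtained during the study including the screening". For non-target nodes, Section 9.4.3.1.2 offers a guide: "Apparent growth is, only as a guide, the growth of long dimension" of at least 50%.

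Extranodal CR requires disappearance, so the shared 1.5 cm cut-off concerns nodes only.

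**The concern.** The permitted spacing is coarse compared with the size on which classification turns. A node of 1.6 cm may be cut by only one or two sections, and the nearest one can miss its centre by up to 5 mm. The reading then falls below the true diameter. Because the entry limit and the nodal CR limit are the same number, a small under-reading is enough to move a node from measurable disease to not enlarged. It also skips PR: a change from 1.6 to 1.5 cm is a 12% fall in the product (1 − 2.25/2.56), far short of 50%.

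ORR is the primary endpoint, with 18 evaluable patients planned (Section 5.2), so one misclassified patient moves it by 1/18 = 5.6 percentage points. Independent radiology review (Section 3.4.2) works from the same images and cannot restore sections that were never produced.

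**Working it through.** The plan states no measurement error for CT, so there is no figure to reproduce. The check is geometric.

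**Inputs from the documents:** spacing s up to 1 cm; cut-off 1.5 cm; PD at +50% of the product sum from its lowest value; up to six target lesions, largest first (Section 9.4.2.1.6).

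**Assumptions:** pitch means section spacing; the node is an unchanged sphere of true diameter D; sections are thin; the nearest section is off-centre by u, uniform on 0 to s/2 and independent between scans.

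**Reading on one scan.** The long dimension is L = √(D² − 4u²), and the lowest possible reading is √(D² − s²).

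For D = 1.6 and s = 1, L ≤ 1.5 when 4u² ≥ 2.56 − 2.25 = 0.31, so u ≥ 0.278. The probability is (0.5 − 0.278)/0.5 = 44%.

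For D = 1.7, 4u² ≥ 0.64, so u ≥ 0.4 and the probability is 20%.

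| True D (cm) | Lowest reading, 1 cm | Reads ≤ 1.5, 1 cm | Lowest reading, 5 mm | Reads ≤ 1.5, 5 mm |
|---|---|---|---|---|
| 1.55 | 1.18 | 61% | 1.47 | 22% |
| 1.6 | 1.25 | 44% | 1.52 | 0% |
| 1.7 | 1.37 | 20% | 1.62 | 0% |
| 1.8 | 1.497 | 0.5% | 1.73 | 0% |
| 2.0 | 1.73 | 0% | 1.94 | 0% |

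The upper end of the affected range is √(2.25 + s²): 1.80 cm at 1 cm spacing and 1.58 cm at 5 mm.

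**Repeated scans and several nodes.** Take nodes of 1.6 cm that read over 1.5 cm at screening, and count any single reading of nodal CR. For one node the chance is 1 − 0.557² = 69% by two post-dose scans and 1 − 0.557⁴ = 90% by four. All nodes must fall together, so by four scans it is 58% with two nodes, 31% with three and 3% with six. If a reading must persist to a second scan, the one-node figure over two scans is 0.443² = 20%.

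**False growth.** For a sphere the product is L², so the largest ratio is D²/(D² − s²).

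- At D = 1.6 and s = 1 this is 2.56/1.56, or +64%. At 5 mm it is 2.56/2.31, or +11%.
- Reaching +50% needs D² ≤ 3s², so D ≤ 1.73 cm at 1 cm spacing.
- It cannot occur against screening, where the node read over 1.5 cm. At 1.6 cm the most is 2.56/2.25, or +14%, and over all spheres 3.25/2.25, or +44%. A post-dose nadir is needed: at 1.6 cm, 1.31 cm or less (√(2.56/1.5)).
- In simulation, the chance for a sole 1.6 cm target node is about 2% by two post-dose scans and 11% by four. With two nodes it is 0.7% by four scans, and with six about 0.
- The non-target guide of +50% in long dimension needs D ≤ 1.34 cm, so no sphere over 1.5 cm can meet it.

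**Sensitivity.** With contiguous 1 cm slices and a half-intensity edge, a 1.6 cm sphere reads from √(2.56 − 1) = 1.25 to √(2.56 − 0.25) = 1.52 cm. The CR flip remains, but growth peaks at 2.31/1.56, or +48%. In the thin-section model, a node 1.6 cm in plane and 2.4 cm craniocaudally still reads 1.5 cm or less on 17% of scans, with growth of at most 21%. One only 1.2 cm craniocaudally can show growth of up to 227%.

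**The case against.** The strongest reply is that a nodal reading is not a response. Table 8 also requires extranodal sites, spleen and liver, skin, blood and marrow to be normal for CR. Targets are taken largest first, and Section 9.4.2.1.6 asks for lesions suited to exact, continuous measurement. With several small nodes a joint flip soon becomes unlikely. The 1 cm figure is a ceiling, and sites may already scan more finely. Sphericity and thin sections are assumptions, and with thick slices a 1.6 cm node often fails to qualify at screening at all. Part of the cause is the shared cut-off rather than the spacing.

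Most of this stands and limits the scope. It does not remove the problem: inclusion criterion 2 allows entry with a single measurable lesion, and the flip survives both the thick-slice model and the taller node.

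A reader might also infer that slice position readily produces false progression. The documents do not support that: it takes a low post-dose nadir and essentially a sole target node, and the thick-slice model does not reach 50% at 1.6 cm. Section 2.6 also rests PD on local radiology together with clinical judgement. Nor can slice position alone create PR in a 1.6 cm sphere, whose product falls by at most 1/2.56 = 39%.

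**Conclusion.** The concern holds for nodal CR. At the coarsest spacing allowed, an unchanged node of about 1.5 to 1.80 cm can read as nodal CR through slice position alone: 44% of scans at 1.6 cm, 20% at 1.7 cm and none above 1.80 cm. This rests on a spherical node, thin sections and random position.

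ORR is affected only in patients whose remaining disease is one or a few such nodes. A reader might conclude that the trial's ORR is materially inflated. That cannot be shown, because the documents give neither the distribution of node sizes nor the spacing sites actually use. False 50% growth is a secondary, model-dependent risk. The point is a cheap improvement to how the primary endpoint is measured, and does not show the design to be invalid.

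**What to change.** In Section 9.4.2.1.1, require section spacing or reconstruction of 5 mm or less for neck, chest, abdomen and groin, at screening and at every later CT. Section 2.6.1 lets routine-care scans serve as screening, so have any with wider spacing reconstructed at 5 mm or less where the raw data allow. Where they do not, flag the patient and show ORR with and without CRs that rest only on nodes of 1.5–1.8 cm at screening. For these patients, Section 9.4.3.1 should say that finer follow-up imaging is an accepted departure from the screening method.

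A 2.0 cm minimum for target lesions on wider-spaced scans may look like an alternative, but I would not add it. It conflicts with Section 9.4.2.1.6, which takes all measurable lesions when there are fewer than six. It could also affect eligibility under inclusion criterion 2, and it leaves non-target nodes uncovered.

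The cost is a short edit to Appendix D, more images per read, and some routine-care scans that cannot be obtained at finer spacing. No additional scan visits are needed. A small range, 1.5–1.58 cm, remains because the two cut-offs coincide.
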